## 5.8 Duration of Study Participation

Study participation may conclude when any of the following occur:

- Completion of study activities (treatment and follow-up)
- Participant withdrawal (see [Section 16.5](#)).
- Participant is lost to follow-up. All attempts to contact the participant must be documented.
- At the discretion of the investigator for safety, behavioral or administrative reasons

Documentation of the reason for discontinuing study participation and the date effective should be made in the medical record and appropriate eCRF. The COH DCC should be promptly notified of the change in participant status.

## 5.9 Supportive Care, Prohibited Medications and Concomitant Therapy

Participants must be instructed not to take any additional medications (including over-the-counter products) during the trial without prior consultation with the investigator.

Participants should not consume grapefruit, grapefruit products, Seville oranges (including marmalades containing Seville oranges), or star fruits while receiving protocol therapy.

With the exception of prohibited therapies listed in [Section 5.9.1](#), participants should receive appropriate supportive care measures as deemed necessary by the treating investigator per institutional standards. TLS prophylaxis guidelines are detailed in [Section 5.9.3](#). Examples of prohibited and cautionary medications are listed in [Appendix D](#).

### 5.9.1 Prohibited and Cautionary Agents

#### Prohibited Agents

The following are prohibited until from Day 1 of protocol therapy to 30 days post last dose.

- Live virus vaccines
- Other anticancer agents
- Other investigational therapy/agent
- Herbal medications

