### 3.2 Exclusion Criteria

#### Previous therapies

- 1. Bcl2 inhibitors
- 2. Any systemic anti-lymphoma therapy, including monoclonal antibody within 28 days or 5 half-lives (whichever is shorter) of initiating protocol therapy
- 3. Radiation and/or surgery (except lymph node or other diagnostic biopsies) within 14 days prior to Day 1 of protocol therapy.
- 4. Short course systemic corticosteroids for disease control, improvement of performance status or non-cancer indication within 7 days prior to Day 1 of protocol therapy. Stable ongoing corticosteroid use (i.e. at least 30 days) up to an equivalent dose of 20 mg of prednisone is permissible.
- 5. Strong or moderate CYP3A inhibitors within 7 days prior to Day 1 of protocol therapy.
- 6. Strong or moderate CYP3A inducers within 7 days prior to Day 1 of protocol therapy.
- 7. P-gp inhibitors within 7 days prior to Day 1 of protocol therapy.

\_\_\_8. Narrow therapeutic index P-gp substrates within 7 days prior to Day 1 of protocol therapy.

\_\_\_9. Any other investigational agent or used an investigational device within 21 days prior to Day 1 of protocol therapy.

Other illnesses or conditions

\_\_\_10. Prior surgery or gastrointestinal dysfunction that may affect drug absorption (e.g., gastric bypass surgery, gastrectomy)

\_\_\_11. Active human immunodeficiency virus (HIV) or hepatitis C virus (HCV) or hepatitis B virus (HBV). Subjects who have an undetectable HIV viral load with CD4 > 200 and are on HAART medication are allowed. Subjects who are positive for hepatitis B core antibody or hepatitis B surface antigen must have a negative polymerase chain reaction (PCR) result before enrollment. Those who are PCR positive will be excluded. Patients who have had Hepatitis C but have finished treatment and are PCR negative will be allowed. (Testing to be done only in patients suspected of having infections or exposures).

\_\_\_12. Concurrent malignancy requiring active therapy.

\_\_\_13. Known central nervous system or meningeal involvement (in the absence of symptoms, investigation into central nervous system involvement is not required).

\_\_\_14. Congestive heart failure (CHF) that meets New York Heart Association (NYHA) Class II to IV definitions (See [Appendix E](#)).

\_\_\_15. Patients with known cardiac abnormalities such as:

- Congenital long QT syndrome
- QTc (Corrected QT interval on ECG) interval >480 milliseconds
- Any cardiac arrhythmia requiring anti-arrhythmic medication.

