#### **5.7 Follow-Up**

Following completion of protocol therapy, all participants will enter follow-up for up to 24 months after ending protocol treatment. This is comprised of:

- **Follow-up for safety**- All participants will be followed until resolution or stabilization of reportable AEs occurring during protocol therapy or starting within 30-days post last dose of protocol therapy. Refer to [Section 7.7](#) for reporting details.
- **Follow-up for response** for those who have yet to have disease progression.
- **Follow-up for survival** - for those who initiated an anti-cancer therapy or have disease progression.

Assessment time points and windows are detailed in [Section 10.0](#).

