### 7.1 General Information

- Baseline values are from screening evaluations.
- For supportive care guidelines see [Section 5.9](#).
- Venetoclax doses missed for toxicity will not be made up.
- Romidepsin doses missed for toxicity will not be made up.
- Permanently **discontinue protocol therapy** if:
  - Participant requires a dose reduction and is already on 100 mg/day of venetoclax
  - Participant requires a dose reduction and is already on 10 mg/m^2 romidepsin
  - Unable to resume treatment within 14 days after last dose of venetoclax
- If the venetoclax dose was reduced during Cycle 1, intra-patient daily re-escalation to steady-state venetoclax dose may be permitted in the absence of a recurrence of the toxicity that led to the reduction following consultation with the Study PI.
- The initiation of a new cycle may be delayed for up to 7 days with written approval from the Study PI in circumstances where the participant is unable to come to the clinic as planned to initiate the new cycle (e.g. planned vacation by participant, lack of transportation etc.).\*

\*If prior approval from the Study PI is obtained, then these modifications will not be considered a protocol deviation. The Study PI will document assessment of the impact of these determinations on the study design, objectives and endpoints or risk to participants. If any modifications to the treatment plan might affect the study design, objectives, and endpoints, or impact the risk of participants, a single subject exception will be sought by the IRB. If the treating investigator is the Study PI, the determination and the rationale for the determination will clearly be documented in the source document(s).

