### **8.1.10 Supplier**

The investigational venetoclax will be supplied free of charge by AbbVie.

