- d. Cycle 1 Day 1 is defined as the day of venetoclax and romidepsin initiation. Delay the Cycle 1 Day 1 dose if the participant is experiencing laboratory TLS as defined in [Appendix B](#).
- e. Assessments must be **performed and reviewed within 72 hours prior** to the C1D1 venetoclax dose (except [tumor imaging](#)).
- f. Cycle 1 Day 2-7 ( $\pm$  2 hours) laboratory assessments must be performed and reviewed prior to administration of the Cycle 1 Day 2-7 venetoclax doses.
- g. *End of protocol therapy (EOT) assessments* to be performed no later than 7 days after decision to end treatment (except tumor imaging); assessments performed after last dose of study agent and within 7 days of the decision to end treatment may serve as EOT assessments. **NOTE:** Tumor imaging performed after last dose of study agent and within 28 days of the decision to end treatment may serve as EOT imaging assessment.
- h. *Safety visit* to occur 30 (-2/+7) days post-last dose of protocol therapy. Expedited reporting will occur during this period (See [Section 7.7.2](#)). Safety follow-up may be extended until resolution/stabilization of reportable AEs.
- i. For participants yet to progress, Response Follow-up will occur every 2 months (+/- 7 days) from the day of last response evaluation until progression or the initiation of a new therapy.
- j. Participants who end Response Follow-up will enter Survival Follow-up. Survival assessment to occur bi-annually or as requested by the Study PI via medical record review, review of social security registry, or telephone call.
- k. *Informed consent* process to be fully documented (see [Section 16.4](#)). Informed consent must occur prior to any research only (non-SOC) screening procedures.
- l. *Medical history* to include a review of treatment history, any ongoing medical conditions and medical history pertaining to eligibility on study and involvement during study
- m. *Eligibility criteria* are detailed in [Section 3.0](#).
- n. *Registration* into a COH clinical trial management system (CTMS).
- o. *Standard physical exam* includes weight and skin analysis.
- p. *Vital signs*: heart rate, blood pressure, respiration rate, and temperature.
- q. *Concurrent medications* and reason for administration to be documented from within 10 days prior to protocol therapy up to 30-days-post last dose visit. See [Section 5.9](#) for concomitant medication restrictions and guidelines.

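### Section 5.9.1 bars other anticancer and investigational agents for 30 days after the last dose, with no exception for a patient taken off treatment for progression

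*Combined protocol and SAP*

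**What the plan says.** Section 5.9.1 introduces its prohibited list with "The following are prohibited until from Day 1 of protocol therapy to 30 days post last dose". Four classes follow: live virus vaccines, other anticancer agents, other investigational agents, and herbal medications. All four get the same window, and no class carries an exception.

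Section 5.6 lists disease progression first among the reasons for ending protocol therapy and then sends the patient to End of Treatment (EOT) assessments. Section 5.7 provides survival follow-up "for those who initiated an anti-cancer therapy or have disease progression". Note i to the study calendar (Table 10.0) continues response follow-up "until progression or the initiation of a new therapy". Note g allows up to 7 days from the decision to stop for EOT assessments. For imaging it says that a scan taken after the last dose and "within 28 days of the decision to end treatment may serve as EOT imaging assessment".

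Section 15.0 lets the PI deviate when necessary, provided that safety and scientific integrity are not threatened. Section 15.2.1 requires any deviation to be notified to the DSMC and IRB within 5 calendar days.

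**The concern.** The ban runs from the last dose, so it applies after protocol therapy has ended, when the trial drugs have nothing more to offer a patient who has progressed. Eligible patients have already failed at least two systemic therapies (Section 3.1, item 6). The protocol itself describes the prognosis as poor (Section 2.1.1) and the disease as aggressive (Section 2.7). For such a patient the next treatment decision may not wait a month.

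The follow-up sections assume that new therapy will start, but they give no timing. The only written rule for the first 30 days is therefore the prohibition. A site that follows it delays care. A site that does not follow it generates a deviation for a foreseeable and ordinary clinical event. Two sites could reasonably act differently.

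**Working it through.** The 30 days is a stated rule with no formula behind it, so there is no figure to reproduce. The check is a reading of the sections against each other, with one subtraction.

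1. **Does the rule reach a patient with progression?** The window in 5.9.1 ends 30 days after the last dose. Section 5.6 makes progression a cause of the last dose. The opening sentence of 5.9.1 is garbled, but however it is repaired the end point is the same. The rule does reach this patient.

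2. **Is there an exception elsewhere?** Section 5.6 gives reasons for stopping and leads to EOT. Section 5.7 and note i mention new therapy as something that ends response follow-up. Section 5.8 covers the end of study participation. Notes g, h and j cover EOT, the 30-day safety visit and survival status. None of them lifts or shortens the ban.

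3. **How long is the wait?** Wait from the decision to stop = 30 days − days already elapsed since the last dose. Venetoclax is taken daily, so for a patient still on drug when progression is found the wait is 30 − 0 = 30 days. It is shorter if dosing had already stopped. Hence up to 30 days.

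4. **Does safety collection depend on the ban?** Adverse events are recorded to 30 days after the last dose (14.3.1). Serious events in that period are reportable whatever their cause (14.3.2.1). Concomitant medications are documented to the 30-day visit (note q). None of these is conditional on the patient being free of new therapy.

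5. **Does it touch the efficacy results?** Response is assessed until progression (12.1), and progression is the event that ends PFS and duration of response (Table 11.3). Once progression is documented, a new drug cannot change these. Overall survival is followed regardless. The design figures do not involve the post-treatment window either. The rejection probability is the sum over x = 1 to 7 of C(7,x) p^x (1−p)^(7−x) × P(Bin(11,p) ≥ 4−x). It equals 0.0893 at p = 0.10 and 0.8000 at p = 0.30, in line with the stated 10% and 80%.

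6. **Should the ban be lifted for every discontinuation?** No, for two reasons.
   - Lead-in patients are assessed for unacceptable toxicity over two cycles. Events at least possibly related to either drug count (11.2), and two such patients suspend accrual (12.1.1). A patient who stopped early for another reason and started a new drug inside that window could have an event that is hard to attribute but still counts.
   - Table 11.3 and Section 12.5 have no rule for new therapy started before progression, so early release would blur PFS and duration of response.

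   Stopping for progression largely avoids both problems. Section 2.7 places it after at least two cycles, although Section 12.3 also provides for progression before then. The lead-in safeguard in the fix is therefore still needed.

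**The case against.** The strongest defence is that 30 days is the trial's safety window throughout: adverse-event recording, serious-event reporting, the safety visit and medication review all run to about day 30. Keeping other active drugs out of that window makes late toxicity easier to attribute, which matters with 18 evaluable patients and a safety objective. The defence would add that sites will read Section 5.7 and note i as permission, that Section 15.0 gives the PI discretion, and that patients may withdraw (17.5).

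Part of this stands. Urgent treatment is not blocked, and the loss of clean attribution is a real cost. But 5.9.1 does not give attribution as its purpose, and collection to day 30 continues with or without the ban. Sections that mention new therapy without a date do not override an explicit prohibition. Discretion and withdrawal are case-by-case routes, and withdrawal can cost follow-up data.

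A reader might also infer that every early start needs prior IRB approval under Section 15.2.2. The documents do not settle that. Section 15.1.2 confines planned deviations to circumstances that could raise patient risk or alter protocol integrity, and needed treatment after progression arguably does neither. The 5-day notification of a deviation is the firmer burden.

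**Conclusion.** The point holds as a defect in a stated rule. Followed literally, 5.9.1 makes a patient with progression wait up to 30 days from the last dose for next-line therapy, or turns an earlier start into a deviation. Only patients who would begin new therapy inside that window are affected. The documents give no basis for estimating how many, so no number is offered. Response rate, type I error and power are unchanged. This is a cheap improvement to care after treatment and to deviation handling.

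Two stronger readings are tempting and should not be drawn.

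- **That the ban exceeds the protocol's own entry washouts by a measurable number of days.** Exclusion 9 bars "Any other investigational agent or used an investigational device within 21 days prior to Day 1 of protocol therapy", and exclusion 2 bars anti-lymphoma therapy "within 28 days or 5 half-lives (whichever is shorter) of initiating protocol therapy". These rules limit carry-over into the trial, which is a different purpose. The second prints no figure for venetoclax, and no entrant could have one, because exclusion 1 bars prior Bcl2 inhibitors. The gap also depends on the rule chosen: 30 − 21 = 9 days under exclusion 9, but 30 − 28 = 2 days under exclusion 2 for a long half-life agent.
- **That a patient removed under the Section 7.1 criterion "Unable to resume treatment within 14 days after last dose of venetoclax" has already served part of the wait.** That is true only if romidepsin had stopped too. Section 5.2 lets a cycle start while either drug is held, and the metabolic and tumor lysis rows of Section 7.2 show no romidepsin hold.

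**What to change.** Split the list in Section 5.9.1.

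- Keep Day 1 to 30 days after the last dose for live virus vaccines and herbal medications.
- For other anticancer agents and other investigational agents, keep the same window and add: *except that, after documented disease progression and permanent discontinuation of protocol therapy, new anticancer or investigational therapy may start when clinically indicated, with EOT assessments done first where feasible.*
- For discontinuation without progression, keep the 30-day rule unless the treating physician, in consultation with the Study PI, judges earlier therapy clinically necessary.
- State that lead-in patients still inside the two-cycle window continue to be assessed for unacceptable toxicity under Section 11.2 after any new therapy starts.
- Record the new agent and its start date in the concomitant medication record, continue adverse-event and serious-event collection to day 30, and flag events that begin after new therapy.

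The cost is a short rewording and one flag. The flag can be derived from the new agent's start date and the event's time of onset, which Section 12.5 already summarizes. No visit or procedure is added. The downside is that some events in the 30-day window will overlap with new therapy and be harder to attribute.

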#### Prohibited Agents During Cycle 1 and Cautionary Thereafter with Venetoclax Dose Reductions

- Strong CYP3A inhibitors
- Prohibited during Cycle 1 and consider alternative medications. If subject requires use of these medications after Cycle 1, use with caution and reduce the venetoclax dose by at least 4-fold during co-administration.
- Moderate CYP3A inhibitors or P-gp inhibitors
- Prohibited during Cycle 1 and consider alternative medications. If subject requires use of these medications after Cycle 1, use with caution and reduce the venetoclax dose by 2-fold during co-administration.

After discontinuation of CYP3A inhibitor, wait for 2 to 3 days before venetoclax dose is increased back to the initial maintenance/target dose. Examples of moderate and strong CYP3A inhibitors are found in [Appendix D](#)

- Strong and moderate CYP3A inducers
  - Prohibited during Cycle 1. Consider alternative medications. If subject requires use of these medications after Cycle 1, use with caution as they may reduce venetoclax exposure and efficacy.

#### Cautionary Agents

- Warfarin and coumarin derivatives
- P-gp substrates
- BCRP substrates
- OATP1B1/1B3 substrates
- BCRP inhibitors

#### 5.9.2 Supportive Therapy for Romidepsin Infusions

- 30 min prior: 5-HT3 receptor antagonist
  - The recommended agent/dose is Zofran 16 mg IVPB or equivalent
- Dexamethasone 10 mg IVPB

#### 5.9.3 Tumor Lysis Syndrome (TLS) Prophylaxis Guidelines

To mitigate the risk for TLS all participants will initiate TLS prophylaxis and undergo monitoring (see [Table 5.9.1](#)). Consider all participant co-morbidities before final determination of prophylaxis.

**Table 5.9.1. Recommended TLS Prophylaxis Pre-Cycle 1 and Blood Chemistry Monitoring During Cycle 1**

Recommended TLS Prophylaxis		Blood Chemistry Monitoring c and Frequency
Hydration a	Anti-hyperuricemics b	
Oral (1.5-2 L) and intravenous (150-200 mL/hr as tolerated)	Allopurinol; consider rasburicase if baseline uric acid is elevated	
 
• Cycle 1-Day 1-8: Pre venetoclax dosed, and post-dose at 6-8, 24 (<math>\pm</math>2) hours for each dose level increase. Next dose should not be administered until 24 h blood chemistry values are evaluated.
 
 
****NOTE: Cycle 1 post-dose Day 1-8 blood chemistry must be reviewed in real-time unless stated otherwise.****

a Administer intravenous hydration for any patient who cannot tolerate oral hydration. IV hydration must be initiated the night before dosing and continued for 24 hours after dose.  
b Start allopurinol or xanthine oxidase inhibitor 2 to 3 days prior to initiation of venetoclax.  
c Evaluate blood chemistries (potassium, uric acid, inorganic phosphorus, calcium, and creatinine)  
d Pre-dose blood collection is to be performed within 4 hours from venetoclax administration.

The management recommendations below focus on the minimum initial responses required. Any abnormal chemistry tests should be corrected promptly.

If a diagnosis of TLS is established, ongoing intensive monitoring and multi-disciplinary management will be per institutional practice. Refer to [Table 7.2.1](#).

##### *5.9.3.1 Hyperkalemia (including rapidly rising potassium)*

- For potassium increase  $\geq 0.5$  mmol/L from baseline, or any value  $> 5.0$  mmol/L, recheck potassium, phosphorus, uric acid, calcium and creatinine and follow first guideline.

*If Potassium  $\geq 0.5$  mmol/L increase from prior value (even if potassium within normal limits [WNL])*

- Recheck potassium, phosphorus, uric acid, calcium and creatinine in 1 hour.
  - If further  $\geq 0.2$  mmol/L increase in potassium, but still  $<$  upper limit of normal (ULN), manage as per potassium  $\geq$  ULN (see below).
  - Otherwise recheck in 1 hour.
- Resume per protocol testing if change in potassium is  $< 0.2$  mmol/L, and potassium  $<$  ULN, and no other evidence of tumor lysis.
- Per investigator discretion recheck prior to hospitalization.
  - If stable or decreased, and still WNL, hospitalization is at the discretion of the investigator.
  - Potassium, phosphorus, uric acid, calcium and creatinine must be rechecked within 24 hours.

*If Potassium  $\geq$  ULN*

- Perform EKG and commence telemetry.
- Consult Nephrology (or other acute dialysis service).
- Administer Kayexalate 60 g (or Resonium A 60 g).
- Administer furosemide 20 mg IV  $\times 1$ .
- Administer calcium gluconate 100 to 200 mg/kg IV slowly if there is EKG/telemetry evidence of life threatening arrhythmias.
- Recheck potassium, phosphorus, uric acid, calcium and creatinine in 1 hour.
  - If potassium  $<$  ULN 1 hour later, repeat potassium, phosphorus, uric acid, calcium and creatinine 1, 2 and 4 hours, if no other evidence of tumor lysis.

*If Potassium  $> 6.0$  mmol/L(6.0 mEq/L) and/or symptomatic (e.g. muscle cramps, weakness, paresthesias, nausea, vomiting, diarrhea)*

- Perform EKG and commence telemetry.
- Nephrology (or other acute dialysis service) assessment with consideration of initiating dialysis.
- Administer Kayexalate 60 g (or Resonium A 60 g).
- Administer furosemide 20 mg IV  $\times 1$ .
- Administer sodium bicarbonate 1 to 2 mEq/kg IV push.
  - If sodium bicarbonate is used, rasburicase should not be used as this may exacerbate calcium phosphate precipitation.
- Administer calcium gluconate 100 to 200 mg/kg IV slowly if there is EKG/telemetry evidence of life threatening arrhythmias. Do not administer in same IV line as sodium bicarbonate.
- Recheck potassium, phosphorus, uric acid, calcium and creatinine.

